5.2 RATIONALE

Two previous clinical studies of omiganan in rosacea were conducted. CLS001-R-001 was a double-blind, multicenter, randomized, vehicle-controlled, parallel group study in 240 adult subjects with subtype 2 papulopustular rosacea. Subjects were treated for 9 weeks. The primary objective of the study was to evaluate the safety and efficacy of omiganan pentahydrochloride topical gel 1% w/w and 2.5% w/w compared to vehicle gel in subjects with papulopustular rosacea. Eligible subjects were randomized to 5 treatment groups in a 2:2:2:1:1 ratio. The treatment arms were:

- Omiganan pentahydrochloride topical gel, 1% w/w QD
- Omiganan pentahydrochloride topical gel, 2.5% w/w QD
- Omiganan pentahydrochloride topical gel, 2.5% w/w BID
- Vehicle QD
- Vehicle BID

All efficacy variables improved compared with Baseline in all treatment groups in the modified intent to treat (MITT) analysis. The reductions from Baseline tended to be greatest in the omiganan 2.5% QD group; however, there were no statistically significant differences between the active treatment groups and the combined vehicle group for any efficacy variable at the Week 9/end of treatment endpoint for the MITT population.

CONFIDENTIAL

Version Date: 31 March 2017

Analyses of the per protocol (PP) population were supportive of the results for the MITT population. All efficacy variables improved relative to Baseline for all treatments. For the Week 9 analyses, there were statistically significant differences between active and vehicle treatment for change from Baseline in inflammatory lesion count (for omiganan 2.5% QD versus vehicle, in favor of omiganan) and for scaling/peeling (omiganan 2.5% BID versus vehicle, in favor of vehicle).

Further exploratory analyses with comparisons of the treatment groups, stratified by Baseline lesion count, demonstrated a statistically significant difference in the mean change from baseline in inflammatory lesions counts for omiganan 2.5% QD versus vehicle QD in subgroups with more severe rosacea (> 14.5 lesions at baseline). Overall in the MITT population (all subjects), the mean change from Baseline in lesion count at Week 9 for omiganan 2.5% QD and vehicle QD was -5.93 versus -1.50, respectively ($P=0.041$). For subjects with a baseline lesion count >14.5, the mean change in lesion count was -7.58 and +0.63 for 2.5% QD and vehicle QD, respectively ($P=0.013$) at Week 9.

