7.2 SELECTION OF STUDY POPULATION

7.2.1 Inclusion Criteria

Subjects must meet each of the following criteria to be considered eligible for entry into the study:

1. Subjects who provided written informed consent to participate in the study.
2. Healthy, male and non-pregnant female subjects, 18 years of age or older.
3. A diagnosis of papulopustular rosacea with ≥ 30 inflammatory facial lesions (papules, pustules) at Baseline. Subjects must have no more than 2 nodular lesions, at Baseline.
4. Subjects with the presence of telangiectasia at Baseline.
5. Subjects with an erythema score of at least 2 on the Investigator Assessment of Erythema (IAE) scale at Baseline.
6. Subjects with a grade 4 (severe rosacea) on the 5-point Investigators Global Assessment (IGA) scale at Baseline.
7. Non-nursing, female subjects of child bearing potential, who are using a highly effective form of birth control or females not of childbearing potential due to menopause (must be postmenopausal for at least one year).
 - Highly effective methods of birth control are defined as those, alone or in combination, that result in a low failure rate (i.e. less than 1% per year) when used consistently and correctly. Forms of birth control include: Oral (birth control pills), Intravaginal: (e.g. NuvaRing®), Implantable (e.g. Norplant®), injectable (e.g. Depo-Provera®) or transdermal (e.g. Ortho Evra®) contraception; intrauterine device (IUD); double-barrier (diaphragm or condom with spermicidal gel or foam); for two months prior to study enrollment (see exclusion criteria #6) or a vasectomized partner or true abstinence (in line with preferred and usual lifestyle of subject) with an acceptable form of birth control should the subject become sexually active.

CONFIDENTIAL

Version Date: 31 March 2017

Periodic abstinence (e.g., calendar, ovulation, symptothermal, post-ovulation methods) and withdrawal are not acceptable methods of contraception. All female subjects of child bearing potential must undergo an in-office, highly sensitive urine pregnancy test, with a negative result, prior to being randomized to receive study drug. In addition, women of childbearing potential must agree to have a highly sensitive urine pregnancy test at the end of the study.

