7.4.3 Other Signs and Symptoms Assessment

Other signs and symptoms will be assessed at Screening and each double-blind study visit (Baseline, Weeks 1, 3, 6, 9, and 12). The investigator must evaluate the severity of the other signs and symptoms of Rosacea. This should be done after evaluating the IGA and IAE, but before performing the lesion count. The areas that will be evaluated are as follows:

- Telangiectasia
- Scaling/peeling
- Pruritus

The score represents that subject's condition at the time of the evaluation. These signs and symptoms will be assessed using the following scales:

Telangiectasia Scale

Grade	Grading Scale Score	Description: Telangiectasia; fine superficial blood vessels that are visible near the surface of the skin.
None	0	No telangiectasias present on the face.
Mild	1	Some to a few telangiectasias are present on the face.
Moderate	2	Many telangiectasias, easily recognized, and extending to lateral cheeks, chin, or forehead.
Severe	3	Many to numerous telangiectasias over the entire face that blends in or matches with the erythema caused by inflammatory lesions. Few matted and dense cluster of vessels present.

Scaling/Peeling Scale

Grade	Grading Scale Score	Description: Scaling/ Peeling
None	0	No evidence of scaling.
Mild	1	Cracks easily evident.
Moderate	2	Marked cracks, wide and deep; scales large and lifting.
Severe	3	Large lifting scales, barely attached or shedding.

CONFIDENTIAL

Version Date: 31 March 2017

Pruritus Scale

Grade	Grading Scale Score	Description: Pruritus
None	0	No itching.
Mild	1	Occasional, slight itching; not really bothersome.
Moderate	2	Constant or intermittent itching that is somewhat bothersome.
Severe	3	Bothersome itching; excoriations of the skin from scratching may be present.

These clinical signs and symptoms of Rosacea: telangiectasia, scaling/peeling and pruritus are considered as part of the baseline and ongoing efficacy evaluation. If a new Rosacea sign or symptom or worsening of a Rosacea sign or symptom is believed by the investigator to be related to the study drug and not the disease, then it should also be recorded as an AE.

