### **5.3 Efficacy Endpoints**

The co-primary endpoints are:

- The absolute change from baseline to Week 12 in inflammatory lesions (papules and pustules).
- IGA at Week 12: 2 point reduction; Clear or Almost Clear (IGA 0, 1).

Secondary endpoints are:

- The absolute change from baseline to Week 9 in inflammatory lesions (papules and pustules).
- The absolute change from baseline to Week 6 in inflammatory lesions (papules and pustules).
- IGA at Week 9: 2 point reduction; Clear or Almost Clear (IGA 0, 1).
- IGA at Week 6: 2 point reduction; Clear or Almost Clear (IGA 0, 1).

Exploratory endpoints:

- The absolute change from baseline to Weeks 1 and 3 in inflammatory lesions (papules and pustules).
- Percentage of subjects with an IGA of clear or almost clear (0 or 1) at Weeks 1 and 3.
- Percentage of subjects with a 2 point IGA reduction at Weeks 1 and 3.
- Percentage of subjects with an Investigator Assessment of Erythema (IAE) of clear or almost clear (0 or 1) at each visit.
- Percentage of subjects with telangiectasia score of none or mild (0 or 1) at each visit.
- Percentage of subjects with scaling/peeling score of none or mild (0 or 1) at each visit.
- Percentage of subjects with pruritus score of none or mild (0 or 1) at each visit.

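### The none-or-mild endpoints for scaling/peeling and pruritus count subjects who start without the sign as successes and cannot register none-to-mild worsening; for telangiectasia the issue is limited to subjects who start at mild

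*SAP*

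**What the plan says.** SAP 5.3 lists, among the exploratory endpoints, "Percentage of subjects with scaling/peeling score of none or mild (0 or 1) at each visit". It applies the same cut to pruritus and to telangiectasia, and protocol 7.7.6.3 has the same three. None carries a baseline condition or a change from baseline.

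Entry requirements differ by sign (protocol 7.2.1):

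- Scaling/peeling and pruritus: no criterion.
- Telangiectasia: "Subjects with the presence of telangiectasia at Baseline". Score 0 means none, so eligible subjects start at 1 or higher.
- Erythema: "Subjects with an erythema score of at least 2 on the Investigator Assessment of Erythema (IAE) scale at Baseline". Nobody eligible starts as a responder on the erythema 0/1 endpoint.

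On the scaling/peeling scale in protocol 7.4.3, mild (score 1) is described as "Cracks easily evident".

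SAP 5.4.5 plans change or shift summaries for vital signs and laboratory values only. Under protocol 7.4.3 and 7.5.6.1, a new or worse rosacea sign becomes an adverse event when the investigator attributes it to study drug rather than to the disease.

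**The concern.** An endpoint that asks only whether a subject is at 0 or 1 mixes two groups: those who had a sign and lost it, and those who never had it to a degree that counts. The second group cannot improve on this measure, so it pulls the arms together.

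The measure is also blind to movement between 0 and 1. For scaling, that is the difference between no scaling and readily visible cracks. Local tolerability of a leave-on facial gel is a question the trial could answer, because these signs are scored by arm at every double-blind visit. As planned, the summaries discard the mildest step of worsening. The adverse-event route recovers it only when the investigator, who is blinded, attributes the change to the gel.

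The Phase 2 history gives a reason to look. Protocol 5.2 reports that in the first rosacea study scaling/peeling differed significantly in favor of vehicle for the 2.5% twice-daily regimen, in the per-protocol population at Week 9.

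**Working it through.** **The plan's own figures.** The documents state no effect size, baseline distribution or power for the sign endpoints. The only usable planning input is the arm size of 225 (SAP 5.1). It reproduces: a two-sided Fisher's exact test at 17% versus 6% with 225 per arm has 95.1% power by exact enumeration. It does not depend on the signs.

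**What the endpoint measures.** Let f be the share at 0 or 1 at baseline (equal in expectation across arms), Δ the difference in reaching 0/1 among subjects who start at 2 or 3, and w the share of the baseline 0/1 group who move to 2 or 3 in each arm. Then:

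observed difference = (1 − f) × Δ − f × (w_omiganan − w_vehicle)

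Two results follow without any assumption about numbers:

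- A 0-to-1 change enters neither Δ nor w, so it contributes exactly zero. The same is true of 1-to-0 improvement and 2-to-3 worsening.
- Worsening from 0 or 1 to 2 or 3 enters w and does lower the percentage.

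For telangiectasia nobody eligible starts at 0, so none-to-mild worsening from baseline cannot occur. There, f is simply the share who enter at mild.

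**Size of the attenuation (illustration).** Assume 60% versus 40% of subjects starting at 2 or 3 reach 0/1, and w = 0 in both arms. Power is the two-sided 5% normal approximation:

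Φ{ [d − 1.96 √(2p̄(1 − p̄)/n)] / √([p₁(1 − p₁) + p₂(1 − p₂)]/n) }

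Example at f = 50%: the all-subject rates are 0.5 + 0.5 × 0.6 = 0.80 and 0.5 + 0.5 × 0.4 = 0.70, so d = 0.10. With n = 225, (0.10 − 1.96 × 0.0408)/0.0406 ≈ 0.49, which gives 69%. In the affected subset, d = 0.20 and n = 225 × 0.5 = 112.5, which gives 86%.

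| f (at 0/1 at baseline) | All-subject difference | Power, 225 per arm | Power, baseline ≥ 2 only (difference 20 points) |
|---|---|---|---|
| 0% | 20 points | 99% | 99% |
| 25% | 15 points | 91% | 96% |
| 50% | 10 points | 69% | 86% |
| 70% | 6 points | 43% | 65% |
| 80% | 4 points | 29% | 48% |
| 90% | 2 points | 16% | 26% |

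With 70% versus 50% instead and f = 75%, the all-subject difference is 0.25 × 20 = 5 points. Power is 42% for all subjects and 58% in the subset.

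**Size of the blind spot (illustration).** Assume 30% versus 10% of subjects starting at 0 go to mild, with no other worsening. The 0/1 endpoint shows a difference of 0. A worsened-by-one-grade rate over all subjects would show:

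- 30% start at 0: 9% versus 3%, 6 points, power 77%
- 50% start at 0: 15% versus 5%, 10 points, power 95%
- 70% start at 0: 21% versus 7%, 14 points, power 99%

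**Whether another planned output fills the gap.** Protocol 7.7.12 mentions shifts in physical examinations, but SAP version 2.0 removed those summaries because only examination dates are collected. The subject-reported signs and symptoms in SAP 5.4.2 are baseline only. That leaves adverse-event tables, which depend on attribution.

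**The case against.** The case for leaving the plan alone is substantial.

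- **The Phase 2 result is thin.** A reader might infer that the plan hides a known scaling harm. The documents do not support that. The difference was one per-protocol comparison on a twice-daily regimen. The modified intent-to-treat analysis found no significant difference on any efficacy variable, and this trial applies the gel once daily.
- **Worsening is not wholly invisible.** Movement from 0 or 1 to 2 or 3 lowers the percentage. Subjects are asked about adverse events at each visit, the severity scale includes mild, and events are tabulated by severity and relationship.
- **The comparison is not biased toward omiganan.** Subjects who start at 0 or 1 are balanced by randomisation, so they attenuate a difference rather than create one.
- **The baseline share may be displayed.** Protocol 7.4.3 counts Baseline among the double-blind visits, so an each-visit table may show f by arm.
- **Power matters little here.** The exploratory endpoints have no named test and sit outside the testing sequence. Every input to the power illustrations is assumed.

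All of this stands, and it limits the claim. It does not close the gap. A table of percentages by visit gives neither the split between 0 and 1 nor the direction of individual change. The adverse-event route omits none-to-mild worsening that a blinded investigator puts down to rosacea.

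**Conclusion.** The point holds as a cheap improvement to exploratory summaries. For scaling/peeling and pruritus, subjects who enter without the sign count as successes, and none-to-mild worsening contributes exactly zero; both follow from the definitions alone. For telangiectasia only the attenuation applies, through subjects who enter at mild. The erythema endpoint is protected by its entry criterion.

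The attenuation factor is (1 − f), provided subjects at 0/1 do not cross to 2 or 3 at different rates by arm. Its size cannot be fixed because the documents give no baseline scores. The power figures only illustrate the mechanism. The Phase 2 comparison is a reason to look, not an established harm of the once-daily regimen. Sample size, alpha and the co-primary and secondary conclusions are untouched.

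**What to change.** In SAP 5.3 and 5.4 and protocol 7.7.6.3, add for scaling/peeling, pruritus and telangiectasia, preferably before the double-blind data are unblinded:

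1. Baseline-to-visit shift tables by arm at Weeks 1, 3, 6, 9 and 12.
2. The number and percentage worsened by at least one grade from baseline, by arm and visit, whatever the attributed cause.
3. The 0/1 rate among subjects with a baseline score of 2 or more, next to the existing all-subject rate.

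The erythema endpoint needs no change. The cost is a few extra exploratory tables from scores already collected. The drawback is the smaller denominator in item 3: if 90% start at 0 or 1, only about 225 × 0.10 ≈ 22 subjects per arm remain, so that rate should be read descriptively beside the all-subject rate.

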### **5.4 Statistical Analysis**

#### **5.4.1 Unblinding at Completion of Double-Blind Study Period**

Unblinding of the study will occur when all double-blind study data has been entered into the database and the double-blind database is locked. The open-label extension may be ongoing at the time of double-blind lock and unblinding.

#### **5.4.2 Subject Accounting, Demographic, and Baseline Characteristics**

Demographic, baseline characteristics (including vital signs and laboratory parameters), medical history, baseline subject reported signs and symptoms of rosacea, and prior and

concomitant medications will be summarized by treatment. Study completion status and reasons for discontinuation will also be displayed by treatment.

Previous rosacea therapies taken within the last five years will only be presented in the listings.

#### **5.4.3 Efficacy Analysis**

The co-primary endpoint of absolute change from baseline in inflammatory lesions will be analyzed using an Analysis of Covariance (ANCOVA) model, with treatment as a main effect, and baseline inflammatory lesions and pooled center as covariates. To investigate consistency of efficacy results across study centers, treatment by center interaction will be tested at 0.1 level of significance, and if significant, it will be further be explored.

The co-primary endpoint of IGA will be tested in the following manner: the 2 point reduction and the Clear or Almost Clear (0, 1) will be tested using the Hochberg procedure as follows: Statistical significance will be concluded if both endpoints are significant at a two-sided 0.05 level, or if either endpoint is significant at a two-sided 0.025. Both IGA endpoints will be analyzed using a Cochran–Mantel–Haenszel (CMH) test with center as the stratification factor. If the overall IGA response rates are less than 10%, a Fisher’s Exact test will be used to corroborate the CMH test. All tests of the co-primary endpoints will be analyzed.

If the co-primary endpoints of absolute lesion reduction and the two IGA endpoints (2 point reduction, and Clear or Almost Clear (0, 1)) are significant, the secondary endpoints will be tested sequentially in the order listed as follows:

- Test first secondary endpoint at 0.05. If not significant, stop; otherwise,
- Test second secondary endpoint at 0.05. If not significant, stop; otherwise,
- Test third secondary endpoint at 0.05 using Hochberg (similar to the primary method). If not both IGA (0,1) and IGA 2 point reduction are significant, stop; otherwise,
- Test fourth secondary endpoint at 0.05 using the Hochberg method.

For all efficacy analyses, small centers may be pooled in order to ensure sufficient cell counts for statistical testing.

Subgroup summaries (e.g. Gender, Age, Race, and Center) of the co-primary endpoints will be performed.

[figure not shown]

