7.4.1 Investigators Global Assessment (IGA)

The IGA should be performed at Screening and each study visit (Baseline, Weeks 1, 3, 6, 9, 12, 16, 26, 39 and 52) prior to performing the lesion count. The IGA is intended for the global evaluation of papulopustular rosacea. Background nontransient erythema and telangiectasias should not be assessed as part of the IGA. The IGA score represents the subject's condition at the time of the evaluation.

The following categories will be used from the IGA scale to perform the global evaluation of papulopustular rosacea:

CONFIDENTIAL

Version Date: 31 March 2017

Investigators Global Assessment (IGA) Scale

Grade	Grading Scale Score	Description of Papulopustular Rosacea Disease Status
Clear	0	No inflammatory papules or pustules.
Almost clear	1	Very few with 1 or 2 inflammatory papules/pustules.
Mild	2	Several (3-10) small inflammatory papules/pustules.
Moderate	3	11 to 19 small or large inflammatory papules/pustules and no nodules.
Severe	4	Numerous (≥ 20) small and or large inflammatory papules/pustules, and up to 2 nodules, (at baseline).

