## 5.0 Statistical Methodology

All statistical analyses will be performed using SAS® software version 9.3. Unless otherwise specified, all statistical tests will be two-sided with a significance level of 0.05. Continuous parameters will be summarized by N (number of non-missing observations), mean, standard deviation, median, minimum, and maximum. Categorical parameters will be summarized by count and percent.

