## 7.0 Deviations from the Protocol

Because of the wide range of inflammatory lesions at baseline, the ANCOVA model for change in inflammatory lesions was revised to include a covariate for the baseline inflammatory lesions.

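### Baseline lesion count is likely to be prognostic for IGA response, yet the SAP adjusts only the lesion co-primary for it; the IGA test is valid but gives up a little precision

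*SAP*

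**What the plan says.** Protocol 7.4.1 describes IGA 1 as "Very few with 1 or 2 inflammatory papules/pustules" and IGA 2 as "Several (3-10) small inflammatory papules/pustules". Protocol 7.2.1 admits "Subjects with a grade 4 (severe rosacea) on the 5-point Investigators Global Assessment (IGA) scale at Baseline" who also have "≥ 30 inflammatory facial lesions (papules, pustules) at Baseline", and states no upper limit on the count. So IGA 0/1 corresponds to at most 2 remaining lesions, and a 2-grade reduction to at most 10.

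SAP 5.4.3 analyses change in lesions by ANCOVA with "baseline inflammatory lesions and pooled center as covariates". SAP 7.0 explains the baseline term: "Because of the wide range of inflammatory lesions at baseline, the ANCOVA model for change in inflammatory lesions was revised". For both IGA endpoints, SAP 5.4.3 specifies a "CMH) test with center as the stratification factor", with Fisher's exact test as corroboration if response is below 10%.

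Baseline count is also absent from the IGA imputation model (SAP 6.2: sex and the weekly IGA scores), although the lesion imputation model includes it. Randomization (SAP 3.0) accounts for centre only.

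**The concern.** Baseline IGA is the same for everyone, so it carries no information. Baseline lesion count is the graded measure of how far a subject stands from the IGA cut-offs: from 30 lesions a subject must lose 28 to reach IGA 1, and from 60 must lose 58. If the range of baseline counts is wide enough to justify a covariate in one co-primary analysis, the same variable is a natural covariate for the other, and the SAP gives no reason for leaving it out.

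Two things are at stake. Explainable variation between subjects stays in the error of the endpoint that sets the sample size. A chance difference in baseline count between arms would be corrected in the lesion result but not in the IGA result. The interim futility analysis (SAP 5.4.4) uses the same methods on about 60 subjects per group, where chance imbalance is larger.

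**Working it through.** **1. The plan's own figures.** Inputs from SAP 5.1: IGA 0/1 of 17% versus 6%, 225 per arm, Fisher's exact test. SAP 5.0 sets the level: "all statistical tests will be two-sided with a significance level of 0.05". Exact enumeration gives 95.1% power at 225 per arm. For lesions (13.5 versus 4, SD 12, 95% power), the t-based size is 42.5, so 43 per group. Both stated sizes reproduce, and neither relies on baseline adjustment.

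**2. Reduction needed to respond**, (B − cut-off)/B for baseline count B:

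| Endpoint | B = 30 | B = 60 |
|---|---|---|
| IGA 0/1 (≤ 2 left) | 28/30 = 93% | 58/60 = 97% |
| 2-grade reduction (≤ 10 left) | 20/30 = 67% | 50/60 = 83% |

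In percentage terms the hurdle for IGA 0/1 hardly moves; for the 2-grade reduction it moves more.

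**3. Absolute change with the SAP's own means.** Assume normal change unrelated to baseline: P(IGA 0/1) = 1 − Φ((B − 2 − mean)/12).

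| B | Omiganan (mean 13.5) | Vehicle (mean 4) |
|---|---|---|
| 30 | 1 − Φ(1.208) = 0.1135 | 1 − Φ(2.000) = 0.0228 |
| 40 | 1 − Φ(2.042) = 0.0206 | 1 − Φ(2.833) = 0.0023 |
| 60 | 1 − Φ(3.708) = 0.0001 | 1 − Φ(4.500) < 0.0001 |

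The dependence on baseline is steep. But 30 is the lowest permitted count, so these means cannot yield 17% and 6% overall. Even if everyone entered at exactly 30, the means would have to be 28 − 12 × 0.954 = 16.6 and 28 − 12 × 1.555 = 9.3.

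**4. Gain from adjusting, IGA 0/1.** The documents give no baseline distribution, so it is assumed. Two sets of simulations were run, each with 3,000 trials per scenario, 225 per arm and overall rates held at 17% and 6%.

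- *Set A:* baseline 30 plus a gamma excess of mean 8, 15 or 25; pools of 16. The centre-stratified CMH was compared with the same test on residuals from a pooled (treatment-blind) logistic fit on log baseline count.
- *Set B:* baseline 30 plus an exponential excess of SD 8, 12 or 20; 28 pooled centres with no centre effect and no dropout. The centre CMH was compared with a logistic score test adjusting for baseline count. Response probability was Φ(a − (B − 30)/12) for absolute change, or Φ(a − ln(B/30)/s) for proportional change, with s = 1.0 (all three SDs) or 0.6 (SD 12 only).

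| | Proportional | Absolute |
|---|---|---|
| Set A efficiency ratio | 1.005, 1.018, 1.026 | 1.045, 1.099, 1.188 |
| Set B efficiency ratio | 1.013, 1.021, 1.033; 1.038 at s = 0.6 | 1.058, 1.093, 1.170 |
| Set B power, centre CMH | 95.9–96.7% | 96.1–96.8% |
| Set B power, adjusted | 96.2–96.9% | 97.3–97.8% |
| Set B gain in power | 0.1–0.6 points | 0.7–1.5 points |

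Null rejection was 4.6–5.4% for the centre CMH (set B) and 3.9–5.0% for the adjusted test (set A).

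The absolute column needs large means. At baseline SD 12 it implies 38.8% and 16.7% response at 30 lesions, that is, means of 28 + 12 × Φ⁻¹(0.388) = 24.6 and 28 + 12 × Φ⁻¹(0.167) = 16.4. In the proportional model with s = 1.0 and the same baseline SD, response is 25%/10% at 30 lesions, 17%/6% at 40 and 9%/2% at 60.

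**5. Chance imbalance.** In set B it moved the IGA difference with an SD of 0.27–1.06 points, against an assumed effect of 17 − 6 = 11. The full standard error of the difference is √(0.17 × 0.83/225 + 0.06 × 0.94/225) = 2.96 points. Imbalance therefore accounts for (0.27/2.96)² = 1% to (1.06/2.96)² = 13% of the variance. At 60 per group the SD scales by √(225/60) = 1.94, to about 0.5–2.1 points.

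**The case against.** The strongest reply is that nothing is broken. A randomized, centre-stratified CMH needs no baseline covariate, its error rate is held, and the trial was sized without adjustment. Chance imbalance is ordinary sampling error that the test already allows for. Baseline characteristics are summarised by treatment (SAP 5.4.2), so an imbalance would be visible. All of that stands.

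The reply also rightly limits the evidence. IGA is a separate investigator rating made before the lesion count, with wording on lesion size and nodules, so it is not a fixed function of the count. Treating it as one tends to overstate the link.

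Three stronger readings are tempting, and the documents do not support them:

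- A reader might infer that the IGA test is biased or that 450 is too few. The checks above show neither.
- A reader might infer that the SAP concedes the same reason applies to IGA. SAP 7.0 cites only the wide baseline range, and only for the change-in-lesions model.
- A reader might take the 4–19% gain as following from the sample-size section. Only the SD of 12 comes from there; the means of 13.5 and 4 cannot produce 17% and 6%.

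What survives is that a prognostic variable already collected, and already used for one co-primary, is left out of the other without explanation.

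**Conclusion.** The point holds as a modest loss of precision, not as a flaw in validity. Baseline count is likely to be prognostic for IGA response. How strongly depends on whether lesions fall proportionally or by an absolute amount, which the documents do not say. For IGA 0/1, adjusting is worth about 0.5–4% in efficiency under proportional change and about 4–19% under the less plausible absolute model, or roughly 0.1–1.5 points on about 96% power.

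These figures rest on assumed baseline distributions and change models. The simulation error of a single power estimate is about √(0.96 × 0.04/3,000) = 0.4 points; the tests were compared on the same simulated data, but the smallest gains should be read as close to nil. The 2-grade endpoint is not sized because the documents give no rates for it; step 2 suggests that its dependence on baseline is at least as strong. The change is cheap enough to be worth making before unblinding.

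**What to change.** Before unblinding:

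- **SAP 5.4.3:** for both IGA endpoints, specify a covariance-adjusted CMH stratified by pooled centre with log baseline lesion count as covariate. Keep the unadjusted CMH as supportive.
- **SAP 6.2:** add baseline count to the IGA imputation model, with a matching entry in its MIN, MAX and ROUND lists. The adjusted test still yields a Z score, so the pooling described there can be kept.
- **SAP 5.4.4:** state whether the interim uses the adjusted or the unadjusted test, since it currently inherits the methods of 5.4.3.
- **SAP 7.0:** record the change beside the ANCOVA entry.

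Two alternatives are less suitable. Splitting the CMH strata by baseline half thins pools of 16: simulated relative efficiency for IGA 0/1 was 0.94–0.97 in four of six scenarios and 1.01 and 1.03 in the other two. Conditional logistic regression would move the target to a conditional odds ratio, away from the comparison of response rates.

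The cost is slightly more complex code and the matching edits to SAP 5.4.4 and 6.2. No new data are needed.
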